- Before you start to use a new bottle of Pirinase Hayfever Relief, or if you have not used it for a long time, you should clean the nozzle and pump several times until you get a fine mist.
- Hold the bottle as shown with your forefinger and middle finger on the collar, either side of the nozzle and your thumb underneath the bottle.
- Keeping your thumb still, press down with your finger to pump the spray.
- When doing this make sure you do not point the nozzle at yourself or someone else.
- If the spray still doesn't work, try to clean it as described under the 'To clean the nozzle' section. Do not use any sharp objects because this will destroy the spray mechanism.

[figure not shown]
[figure not shown]
Please turn over →

6200000006215

Using Pirinase Hayfever Relief:

1. Shake the bottle well and remove the dust cap.
2. Blow your nose gently.
3. Use one nostril as shown and put the nozzle in the other nostril. Tilt your head forward slightly and keep the bottle upright. Hold the bottle in your hand and breathe slowly through your nose. While you are breathing in, squirt a spray of fine mist into your nostril by pressing down firmly on the collar with your finger (Picture 4).
4. Breathe out through your mouth. Repeat step 4 to take a second spray on the collar with your finger (Picture 5).
5. Repeat steps 3 to 6 for the other nostril.
6. Remove the nozzle from this nostril and breathe out through your mouth (Picture 5).
7. Repeat steps 3 to 6 for the other nostril.
8. Wash your hands with soap and water. Use a clean tissue or handkerchief and replace the dust cap.

To clean the spray:

1. Take the dust cap and nozzle off (Picture 6).
2. Soak the nozzle and dust cap in warm water for 10 minutes and then rinse under a running tap.
3. Shake off the excess water and allow to dry in a warm place – not too hot!
4. Re-fit the nozzle.
5. If necessary, press the pump down several times until you get a fine mist.

4. Possible side effects

Like all medicines, Pirinase Hayfever Relief can have side effects, but not everyone will experience them.

Common effects (more than 1 in 10 people)

- Nose bleed
- Headache
- Unpleasant taste or smell
- Dryness or irritation in the nose or throat

Very rare effects (less than 1 in 10,000 people)

- Stomach pain, diarrhoea, dizziness, feeling sick, feeling a rash, swelling of the mouth or face or having difficulty breathing.

Stop taking this medicine and tell your doctor if you experience:

- Eye problems such as pain or blurred vision
- Nasal problems such as pain and/or persistent bleeding
- Other side effects which have not been listed
- Skin rashes, which have not been listed

It is important to follow the dose instructions shown in Section 3. Using Pirinase Hayfever Relief at higher doses or for a prolonged period of time can cause a number of changes in your body such as catching in the throat more easily.

If you get any side effects, talk to your doctor, pharmacist or nurse. This includes any possible side effects not listed in this leaflet. You can also report any side effects you experience to the Medicines Commission. You can also report any side effects you experience to the Medicines Commission. You can also report any side effects you experience to the Medicines Commission. You can also report any side effects you experience to the Medicines Commission.

5. How to store Pirinase Hayfever Relief

Keep out of the sight and reach of children.

Do not use this medicine after the 'EXP' date shown on the pack.

Use within three months of first use.

Do not store above 30°C.

6206000006215

## 1. INTRODUCTION

The Medicines and Healthcare products Regulatory Agency (MHRA) has required a post-approval commitment from GlaxoSmithKline Consumer Healthcare (GSKCH) for Pirinase Hayfever Relief for Adults 0.05% Nasal Spray.

Specifically, MHRA has required this study to evaluate consumer compliance with the product labelling of Pirinase Hayfever Relief for Adults 0.05% Nasal Spray over at least 2 allergy seasons for the treatment of seasonal allergic rhinitis including hayfever. The purpose is to obtain real-world information on how consumers are complying with the product labelling. This study will coincide with the launch of Pirinase Hayfever Relief for Adults 0.05% Nasal Spray in the United Kingdom. This Statistical Analysis Plan (SAP) is based on the final study protocol dated March 8, 2016.

### 1.1 STUDY OBJECTIVES

The objective of this study is to evaluate if consumers comply with key warnings and directions on the outer label for selection and use of Pirinase Hayfever Relief for Adults 0.05% Nasal Spray.

#### 1.1.1 Primary Objective

There are 5 primary objectives of this study, listed as follows:

1. To assess if consumers of the correct age use the product: Ages 18 and older
2. To assess the correct frequency of use: No more than 2 sprays in each nostril per day
3. To assess reduction of dose: If symptoms improve, 1 spray in each nostril per day
4. To assess if a physician is consulted before use: if a woman is pregnant or breastfeeding
5. To assess if a physician is consulted: If symptoms have not improved after using for 7 days, a doctor is consulted

#### 1.1.2 Secondary Objective

The two secondary objective of this study are as follows:

1. To assess if consumers do not use the drug if they are taking medications for Human Immunodeficiency Virus (HIV)
2. To assess if a physician is consulted: Not used more than 1 month continuously without consulting a doctor

## 1.2 SUMMARY OF THE STUDY DESIGN

This study is an online survey. Consumers who have purchased and used the product will opt into an online survey by scanning a quick response (QR) code on the product package labelling or through an e-mailed invitation to those who have purchased the product at a Boots Pharmacy, which will also include a link to the survey. The study timeframe is February 15, 2016 to March 31, 2018, approximately 2 calendar years so that data from at least 2 allergy seasons for the treatment of seasonal allergic rhinitis including hayfever are included. The entire study is conducted online. There is no study visits. More detailed information of the list of specific tasks for this study is given in protocol.

## 2. STUDY ENDPOINTS

### 2.1.1 Primary Endpoints

Primary endpoints are comprised of the proportion of consumers who comply with each of the five primary objective endpoints, namely:

1. Proportion of consumers with 18 years of age or older.
2. Proportion of consumers who don't exceed 2 sprays/nosetril per day.
3. Proportion of consumers whose dose is reduced to 1 spray/nosetril per day if symptoms improve.
4. Proportion of female consumers who consulted a Doctor before using the drug if pregnant or breastfeeding.
5. Proportion of consumers who consulted a Doctor if symptoms did not improve after 7 days of use.

### 2.1.2 Secondary Endpoints

Secondary endpoints are comprised of the proportion of consumers who comply with each of the two specified secondary objective endpoints below:

1. Proportion of consumers who don't use the drug because of taking HIV medications.
2. Proportion of consumers who consulted a Doctor if medication is used for more than 1 month continuously.

### 2.1.3 Exploratory Endpoints

Demographic information collected are listed below:

1. Gender
2. Age
3. Race
4. Education
5. Household purchase information (primary purchaser or other)

Additional profiling information collected are listed below:

1. How long they have had allergies
2. What type of allergies they have
3. Typical allergy symptoms
4. How often do they see their doctor

### 3. SAMPLE SIZE AND STATISTICAL POWER CONSIDERATIONS

1,537 consumers were planned to complete the survey. No targeting or enrichment for age, gender, and social backgrounds will be conducted. The demographics will be reported for those who choose to enter the online survey. For the threshold of 80% for success, this sample size of 1537 achieves at least 91% power with an assumed compliance rate of 83.3% for each of these five primary endpoints, and the significance level of 0.05 using a two-sided exact binomial test.

### 4. STATISTICAL ANALYSIS

#### 4.1 GENERAL STATISTICAL CONSIDERATION

All descriptive statistics for continuous variables will be reported using mean, standard deviation (SD), median, minimum and maximum. Categorical variables will be summarized as number and percentage of consumers.

All summary statistics will be reported with the precision as described in Table 1.

Table 1: Reporting Precisions for Summary Statistics

| Statistic          | Degree of Precision  |
|--------------------|--|
| n                  | Integer (no decimal digit)   |
| Mean, Median       | One more decimal place than the raw data.  |
| Standard deviation | Two more decimal places than the raw data.   |
| Minimum, Maximum   | The same as the raw data.  |
| Percentage         | One decimal place, except for 100% and 0% where no decimal will be reported (as written here). |

#### 4.2 ANALYSIS POPULATION

All consumers set and full analysis set are defined for the purpose of analysis.

##### 4.2.1 All Consumers Set

All consumers set includes all consumers who scanned QR code or clicked on survey link.

#### 4.2.2 Full Analysis Set

The full analysis set is defined as all consumers who signed the Participation Agreement and did not answer “yes” to Q1A, Q1B, Q1C or left these questions blank.

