6.1. Study Design

This is an online survey to evaluate consumer compliance with the product labelling for consumers who purchase Pirinase Hayfever Relief for Adults 0.05% Nasal Spray. Consumers will respond to screening criteria and if they qualify for the study, they will complete the online survey related to their use of the drug. After completing the survey consumer participation will be considered complete. Data collection will continue through at least 2 allergy seasons and until 1,537 surveys are completed.

Consumers will access an online survey by scanning a QR code on the product package labelling or through an e-mailed invitation to those who have purchased the product at a Boots Pharmacy, which will also include a link to the survey. The entire study will be conducted online; there will be no study visits.

The specific tasks include the following:

- 1) Consumers who have purchased the product will scan the QR code found on the product package labelling or by accessing the link in the e-mailed invitation.
- 2) A Participation Agreement will be displayed. The consumer will read and sign this Agreement electronically. Anyone who does not sign the Participation Agreement will not be admitted to the survey.
- 3) The online survey will begin with a set of brief screening questions related to the inclusion/exclusion criteria.
- 4) If the consumer qualifies and is interested, he or she will then be invited to complete the online survey. This process is voluntary for all participants.
- 5) The online survey will consist of closed-ended questions related to the consumer's use of the product.
- 6) Demographics and profiling information will be collected.
- 7) If a consumer has not used the product for at least a month when they initially complete the survey, a reminder message will be sent to them at a later time so that they can complete the question related to use after 1 month.
- 8) After completing the survey, consumer participation in the study will be considered complete.

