7.1. Study Population and Setting

1,537 consumers in the UK who have purchased and used Pirinase Hayfever Relief for Adults 0.05% Nasal Spray for at least 7 days will be included in this study. No targeting or enrichment for age, gender, and social backgrounds will be conducted. The demographics will be reported for those who choose to enter the online survey.

The anticipated timeframe is approximately 2 calendar years so that data from at least 2 allergy seasons for the treatment of seasonal allergic rhinitis including hayfever are included. The allergy season in the UK can range from April through September with June often having the highest pollen counts and allergy sales; however, allergy seasons vary. If the sample size is not met within the 2-year period the study may be extended.

This is an all comers study which means that consumers will opt into the survey themselves. Consumers will access the online survey by scanning a QR code on the product package labelling or through an e-mailed invitation to those who have purchased the product at a Boots Pharmacy, which will also include a link to the survey. The population is expected to reflect a real-world population of consumers who will purchase and use the drug.

Inclusion:

A consumer will be eligible for inclusion in this study only if all of the following criteria apply:

1. Consumers will be required to review, and electronically sign a Participation Agreement prior to completing the online survey.
2. Consumers of any age may participate.
3. Consumers who have purchased and used Pirinase Hayfever Relief for Adults 0.05% Nasal Spray for at least 7 days and are willing to participate in the online survey.
4. Consumers of either gender may participate

Exclusion:

A consumer will not be eligible for inclusion in this study if any of the following criteria apply:

1. Anyone who is directly involved with medicines such as doctors, nurses, and pharmacists.
2. Consumers who decline participation in the online survey

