7.6.2. Exploratory analysis

Demographic and baseline characteristics will be summarized for the analysis population using descriptive statistics. Continuous demographic and baseline variables such as age will be reported using mean, standard deviation (SD), median, minimum and maximum. Categorical variables including sex, age group, and race will be summarized as number (percent) of consumers.

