### 4.3 DISPOSITION

A disposition of consumers includes the count and the percentage of consumers in each of the following categories:

- All consumers set (consumers who clicked the survey)
  - All consumers who started the survey (consumers who responded to any of screening questions).
  - Incomplete screening (consumers who started the survey but didn't answer all screening questions)
  - Screen Fails (consumers who answered all screening questions [QA, QB, Participation Agreement, and Q1A, Q1B, Q1C] but did not qualify for the study)
  - Full analysis set
    - Consumers who answered any of the questions from 2 to 10
    - Consumers who answered any of the questions from 11 to 12

Listing of consumers who are not included in the full analysis set will be generated.

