### 4.4 DEMOGRAPHICS

Demographics (gender, age, age group, race, education, household purchase information) will be summarized in all consumers set population using descriptive statistics. Continuous demographic such as age will be summarized with continuous descriptive statistics: mean, standard deviation (SD), median, minimum and maximum. Categorical variables including gender, age group, and race will be analyzed using discrete summary statistics (frequency and percentage).

Listing of demographic information will be generated for full analysis set.

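### Does the loosely worded full analysis set in SAP 4.2.2, or the varying population named for the demographics, put any result at risk?

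*SAP*

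**What the plan says.** SAP 4.2.2 admits to the full analysis set everyone who signed the Participation Agreement and did not answer yes to "Q1A, Q1B, Q1C or left these questions blank". QA and QB are not mentioned.

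SAP 4.3 splits those who started the survey into Incomplete screening, Screen Fails and the full analysis set. It describes screen failures as "consumers who answered all screening questions [QA, QB, Participation Agreement, and Q1A, Q1B, Q1C] but did not qualify for the study". Under the full analysis set it also counts those who answered any of questions 2 to 10, and any of questions 11 to 12.

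On demographics, SAP 4.4 says they "will be summarized in all consumers set population using descriptive statistics", and SAP 4.2.1 defines that set: "All consumers set includes all consumers who scanned QR code or clicked on survey link". The same section then says: "Listing of demographic information will be generated for full analysis set". Protocol 7.6.2 says: "Demographic and baseline characteristics will be summarized for the analysis population using descriptive statistics". Protocol 7.1, repeated in Protocol 7.4 and SAP 3, says: "The demographics will be reported for those who choose to enter the online survey".

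Three rules control who can supply data. Protocol 6.1 step 2 says: "Anyone who does not sign the Participation Agreement will not be admitted to the survey". Step 4 of that section invites only consumers who qualify. SAP 6 blocks progress past an unanswered question, does not impute, and drops missing values.

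**The concern.** The full analysis set carries all five primary analyses (SAP 4.5) and both secondary ones (SAP 4.6), so its membership should be beyond argument. Three things make it look arguable.

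- A consumer who signs, gives no yes to Q1A–Q1C, but fails QA or QB fits both the full analysis set and Screen Fails.
- The blank clause can be read as excluding blanks, as keeping signers with blanks, or as a free-standing alternative that would admit people who never signed.
- The demographics table has no single stated population, and within SAP 4.4 the summary and the listing use different sets.

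At worst, unqualified people would enter the denominators of the compliance rates, the disposition would not add up, and the demographics table would describe people who never took part. Protocol 7.8.1 itself raises external validity, so it matters whom that table describes.

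**Working it through.** **The plan's own figure.** Inputs from SAP 3 and 4.5: n = 1,537, threshold 80%, assumed rate 83.3%, two-sided 5% exact test. The smallest r with P(X ≥ r | 1537, 0.80) ≤ 0.025 is 1,261 (82.04%; tail probability 0.0233). Power = P(X ≥ 1261 | 1537, 0.833) = 0.911, so the stated figure of at least 91% reproduces. It does not depend on the point at issue.

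**Who is admitted on paper.** Let QA/QB be pass, fail or blank; the Agreement signed, declined or blank; and Q1A–Q1C without a yes, with a yes, or blank. That gives 3 × 3 × 3 = 27 patterns, of which one is fully qualified.

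| Reading of the blank clause | Patterns admitted | Qualified | Screen Fail | Incomplete |
|---|---|---|---|---|
| A: blanks excluded | 3 | 1 | 1 | 1 |
| B: signers with blanks kept | 6 | 1 | 1 | 4 |
| C: blank stands alone | 12 | 1 | 1 | 10 |

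So the overlap exists on paper under every reading.

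**Which of these can carry an endpoint answer.** Take the unqualified patterns in turn.

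- *QA/QB failed, signed, no yes to Q1A–Q1C (A, B, C).* If QA and QB come before the Agreement, as SAP 4.3 lists them, and a failing answer ends the survey, this person never signs. If the Agreement comes first, as in Protocol 6.1, the person signs, fails screening and is not invited to the compliance questions (step 4). Either way there is no endpoint answer.
- *QA/QB blank, signed, no yes (A, B, C).* If QA and QB precede Q1A–Q1C, forced response makes this unreachable.
- *Signed, Q1A–Q1C blank (B, C; three patterns).* The person stopped at or before Q1 and cannot reach a later question.
- *Not signed, Q1A–Q1C blank (C only; six patterns).* Not admitted to the survey.

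SAP 6 removes missing values, so none of these people enters a compliance denominator. SAP 4.3 also points to reading A, because Incomplete screening is listed separately from the full analysis set.

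**Demographics.** Protocol 6.1 collects use data at step 5 and demographics at step 6. A consumer who clicked and left has no age, race or education to summarise. With missing values dropped, a summary over all who clicked rests on those who reached step 6. The labels differ, but the people with data are essentially the same. What changes is the N at the head of the table.

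**Stress test, illustrative only.** Start from 83.3% of 1,537, about 1,280 compliant, and suppose k unqualified people did answer an endpoint put to everyone. The rate is 1280/(1537 + k) if none of them complies; limits are Clopper–Pearson 95%.

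| k, all non-compliant | Rate | Lower limit |
|---|---|---|
| 0 | 83.28% | 81.32% |
| 1 | 83.22% | 81.26% |
| 10 | 82.74% | 80.76% |
| 24 | 82.00% | 80.001% |
| 25 | 81.95% | 79.95% |

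If the extra people complied at an assumed 60%, about 92 would be needed: (1280 + 55)/(1537 + 92) = 1335/1629 = 81.95%, lower limit just under 80%. If they complied at 83.3%, the lower limit would not fall. Conditional endpoints have smaller denominators and would move more per person.

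**The case for a change.** The case for an edit is that none of this protection is written into the definition. Neither document gives the wording of QA or QB or states that a failing answer ends the survey, and the two documents order the Agreement and the screening questions differently. SAP 4.2.3 sets protocol deviations aside, so no second rule would catch an ineligible consumer. Two programmers could code different counts, and SAP 7 leaves derivations to a separate specification that should follow the SAP. For demographics, SAP 4.4 disagrees with itself within one section, and two added sentences would cost almost nothing.

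Much of this stands as a comment on drafting. Clearer text would do no harm, and at least two distinct demographic populations are named. What does not stand is the step to a result. A leak needs a survey that lets unqualified people into the compliance questions, contrary to Protocol 6.1 step 4, and no passage shows one. Protocol 7.6 lets the SAP modify the protocol's analysis plans, so SAP 4.4 may choose its own set. The protocol's phrase about those who enter sits beside the statement on no targeting or enrichment, and reads as sampling policy more than as a defined analysis set. A summary and a listing on different sets is a reporting choice.

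**Conclusion.** No change to the plan follows. The definition in SAP 4.2.2 is incomplete and loosely phrased, but SAP 4.3 shows the intent: the full analysis set stands apart from Incomplete screening and Screen Fails, and an analyst would code it that way. No effect on any compliance rate or success decision is shown. The possible effects are on the full analysis set count, the disposition percentages and the N heading the demographics table. Their size cannot be given, because the documents contain no click, screen-failure or blank counts. The SAP 4.3 lines for consumers who answered questions 2 to 10 and 11 to 12 would make surplus members of the set visible.

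This rests on three assumptions: the survey invites only qualifiers, as Protocol 6.1 states; forced response works as SAP 6 describes; and age is recorded with the demographics at step 6, not among the screening questions. If age were asked at screening, unqualified people could supply a value for the age endpoint, but for no other primary endpoint.

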#### 4.2.3 Protocol Deviations

Not Applicable.

### 4.3 DISPOSITION

A disposition of consumers includes the count and the percentage of consumers in each of the following categories:

- All consumers set (consumers who clicked the survey)
  - All consumers who started the survey (consumers who responded to any of screening questions).
  - Incomplete screening (consumers who started the survey but didn't answer all screening questions)
  - Screen Fails (consumers who answered all screening questions [QA, QB, Participation Agreement, and Q1A, Q1B, Q1C] but did not qualify for the study)
  - Full analysis set
    - Consumers who answered any of the questions from 2 to 10
    - Consumers who answered any of the questions from 11 to 12

Listing of consumers who are not included in the full analysis set will be generated.

